days of the ODP intake to describe the study and answer questions. For clients who are entering residential treatment, the RA will contact the residential provider to speak to the client to describe the study and answer questions. For recruiting, we will call the residential provider phone number and ask to speak with individuals in treatment for the Opioid Diversion Program who are ready to be released from treatment. The provider will not be involved in recruiting for the study and will not have knowledge about an individual's decision to learn more about the project and plans to meet with the Research Assistant (RA) at an arranged location, once released. The RA will arrange _____ phone meetings with interested clients; within 4 days of the ODP intake for clients in OP treatment and within 4 days of discharge for clients in residential care. During the scheduled phone meeting, the RA will explain the consent process and steps to complete the virtual Consent form accessed through Qualtrics, describe the project, and answer any questions. The RA will then send the Qualtrics link to the individual's cell, tablet, or PC. Consent as well as responses to the Eligibility Questions (see Eligibility Questions in the Appendix) will be recorded via Qualtrics where participants will click on their responses for consent such as "I agree to participate" or "I do not agree to participate." The RA will confirm the consent agreement to participate in the study by reviewing the Qualtrics data, before calling back to ask if the participant has follow-up questions about the study and to describe the steps to complete baseline data collection. Participation will be completely voluntary and clients will be told that there are no legal consequences for declining participation, including having no effect on ODP status.

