Informed Consent document; an \$80 e-gift card for the time to complete intake surveys at the start of the study and \$40 e-gift cards for completing assessments at week 6 (the midpoint) and week 12 (the end of the intervention period) during the 3-month study (eligible for up to \$160) in the form of electronic gift cards to online merchants (e.g., Walmart, Amazon). Participants who use their own smartphone will get a \$25 electronic gift card each month they participate in the study for messaging and data charges (a total of \$75 for 3 months). Participants will not be responsible for any costs to participate in this study. The *Participant Interview Informed Consent* document will indicate that compensation is a \$20 electronic gift card for completing a scheduled interview with a member of the research team. Participants who volunteer to be interviewed at the end of the study will be contacted by the RA to schedule a virtual interview. Both Consent documents will also have information indicating that participation or lack of participation will not affect the individual's status in the ODP, treatment, or treatment status in any possible way. Therefore, participation will be strictly voluntary and should clients choose not to participate or withdraw from the study at a later time, they may do so without repercussion. Participants can withdraw from the study by contacting the RA or Coach by phone and stating that they wish to stop participating. In cases where the Coach is contacted, the Coach will relay the decision to the RA for administrative purposes. The Consent will explain that the research-issued smart phone equipment will be collected by the RA at a time to be arranged with the participant. The Informed Consents will also describe the confidentiality assurances and the procedures employed to safeguard the data. In particular, it will be explained that information collected will be identified only by a random participant **Research ID** number and research reports will only be in aggregate form, whereby no individual can be identified. Recorded interviews will be redacted and identified only by the Research ID for tracking purposes. No individual data (survey, agency, or recorded opinions) will be reported to the ODP authorities or any other entity. The *Primary Study Informed Consent* will include language to allow release of behavioral healthcare agency data from the substance use treatment provider (providing services as part of the Opioid Diversion Program) to the research team for tracking participants across the 12-week intervention, thus providing treatment performance indicators. The *Primary Study Informed Consent* will also state that behavioral healthcare data will be requested by the research team using a variation of the Research ID (referred to as the **Treatment Code**) to link data to a participant. The Treatment Code is an arbitrary number assigned to each participant by the research team. The Code will be provided to the behavioral healthcare provider in a file that links the Code to the participant's name. Therefore, data requests from the research team will include only the Treatment Code, which providers will use to identify the client from the linking file. Behavioral healthcare providers will use only the Treatment Code in submitting data to the research team. Behavioral agency data will be shared with the research team via upload to TCU Box, a secure online data sharing platform. After an Informed Consent has been administered, the RA will answer questions and the client will then be asked to provide written consent.

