Qualtrics Survey Mid-Intervention battery (T2). Participants will be contacted in week 5 by the RA to schedule a date and time to complete Mid-Intervention assessments battery in Qualtrics on a smart phone. The Mid-Intervention battery (and follow-up survey battery) repeats the baseline measures. To start the survey, The RA will confirm the unique Research ID number with each participant before sending the Qualtrics survey link, and this will be entered on the first Qualtrics screen. To start the survey, the participant will receive an SMS message with the Qualtrics survey link. At this timepoint in the study (and at follow-up), participants will also be asked to complete the Qualtrics version of the Telehealth Usability Questionnaire (TUQ), a 21-item measure rating the telehealth experience. The Qualtrics Survey Mid-Intervention assessment battery is expected to take 60 minutes to complete. Following completion of the battery, participants will receive an electronic \$40 gift card.

Follow-up surveys (T3). Following the same scheduling procedures used for the Mid-Intervention survey battery, participants will be contacted in week 11 to arrange the Follow-up Survey battery, expected to take 60 minutes to complete. Following completion of the assessments, participants will receive an electronic gift card in the amount of \$40. Following completion of the Qualtrics survey, the RA will contact the participants to thank each for their contributions to the project. All individuals will be invited to participate in an interview with a member of the research team. Our goal is to obtain feedback at the study closeout (Time 3) from a minimum of 6-8 participants. Interested participants may have the Participant Interview Informed Consent administered with the Media Authorization at this time, or the RA will schedule another meeting on a date and time that is convenient for the participant to complete the Informed Consent. The RA will FedEx the signed

documents overnight to the IBR research team and enter the information into the tracking spreadsheet, which is then uploaded to TCU Box for download by authorized project staff.

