Individual interviews. A member of the research team will coordinate interview scheduling with the RA, who in turn will text message virtual meeting options to the participant. The scheduled meeting will be confirmed by the RA with both parties. The semi-structured interview with a member of the research team will take via meeting-specific HIPAA compliant Zoom chat or by phone. Audio recordings will be processed at the IBR.

Participants will be advised that all identifying information will be removed from the transcribed interview and no identifying information will be reported for the project.

Interviews are expected to take 30 minutes to complete and participants will receive an electronic gift card (\$20) for their participation. Participants who are interested will receive a Qualtrics link for the Participant Interview Consent and Media Release documents.

Responses will be recorded via Qualtrics where participants will click on their responses such as "I agree to participate" or "I do not agree to participate." Audio files will be transcribed for qualitative analysis. Agency Records. Behavioral healthcare data will be obtained for participants in both conditions.

Participants will authorize the release of these data to the research team by signing the *Primary Study Informed Consent* at the start of the study. As part of the data-sharing piece, the research team will also obtain a Memorandum of Understanding (MOU), signed by the behavioral provider and the T-CAP PI. To request treatment data, the IBR research staff will send via email, monthly requests to providers with an attached Provider Data Request Form (included in the Appendix) for each participant receiving services at their agency. The form will include only a unique identification number (i.e., Treatment Code) which the provider will use to identify the participant. No participant name will appear on the form or in the email.

The form has space for the provider to include the following information items:

- Primary diagnosis
- Level of care (outpatient, intensive outpatient, residential, detox)
- Length of program (number of weeks)
- Treatment initiation date
- Number of sessions scheduled this month
- Number of missed sessions this month
- Drug test results for this month
- Treatment discharge date

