Aim 2: Evaluate the proposed T-CAP measures to assess their performance in gauging the impact of telehealth on initiation of in-person Substance Use (SU) treatment, short-term retention in referred SU treatment, and access to other appropriate treatment services (e.g., MAT). Our multidimensional approach includes data from self-report attendance and treatment engagement, self-report drug use, Coaches' advocate records on number of completed assertive referrals, and agency records from police and BH providers (including intake and during-program UA test results). In order to examine groups differences for intervention completers (C) vs non-completers (NC) (i.e., individuals who do not complete the 7 coaching video calls), group differences using t-tests and chi-square tests and we will estimate effect sizes needed for determining a sample size for a future R01 proposal. To assess potential assignment bias, we will test to see if there are baseline differences in demographics: participant race, gender, age and other demographic characteristics, as well as baseline measures of opioid use frequency and amount will be examined using chi-square and t-tests. Effect sizes will be computed for group differences on multiple outcomes (treatment initiation, retention, referrals to expanded SU service options, missed appointments). Service attendance records will be corroborated monthly with service provider records. Examinations of referrals to MAT and alternative pain management care between the C and NC groups, utilizing agency records data and the Coach tracking, will be conducted using a z-score to test differences in proportions of referral types. This will be calculated for all assertive referrals (resulting in scheduled appointments) collectively for a participant, as well as for different types of services.

Analyses of Secondary outcomes. We will examine differences between C and NC groups on several secondary outcomes. Analyses will typically involve t-tests, chi-square tests, and correlations. For example, we will use t-tests to assess differences between groups on the 3-month follow-up measures

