of treatment motivation and psychosocial function from the TCU Client Evaluation of Self and Treatment (TCU CEST), a widely used form listed on the IBR web page. Validation of recent (last few days) self-reported opioid use will be compared with drug testing outcomes at each assessment time point using McNemar's test for change of state, as well as computing sensitivity and specificity statistics and the kappa statistic as a measure of agreement. We will compare self-report, as well as urinalysis (UA) results from agency drug screens between the two groups.

15. Potential Risks and Precautions to Reduce Risk: Indicate any physical, psychological, social, or privacy risk which the subject may incur. Risk(s) must be specified. Also describe what measures have been or will be taken to prevent and minimize each of the risks identified. If any deception is to be used, describe it in detail and the plans for debriefing.

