surveys are completed using Qualtrics, the resulting data file is not readable until it is uploaded to the secure Qualtrics server on the TCU campus.

Telehealth session data. The 2-question telehealth satisfaction survey completed on a smart phone at the end of each telehealth session will be available for download through the TCAP app to TCU Box, accessible only by the PI and Project Coordinator. The data will be linked to the phone number and will not include any information that can identify the participant.

The phone number in the .csv dataset will be replaced by the Research ID when the data is downloaded by the Project Coordinator at the IBR.

Data from Coaches. Each Coach will need to have a caseload tracking file with participants' name, Research ID, and phone number, accessible on their TCU-owned secure laptop computers in a Master Linking file. Each laptop will be protected by a strong password and the caseload tracking file—a Microsoft Excel database—will be encrypted and protected by a strong password and used for documenting assertive referrals and other support services (e.g., assistance with obtaining clothing, housing, or transportation) for individual participants, as well as case notes on MI telehealth sessions. The tracking files maintained by Coaches will be uploaded to TCU Box on a weekly basis for the duration of the study. Downloaded caseload tracking files will be stored at the IBR on a TCU-secure computer accessible by authorized IBR researchers; tracking files will be separate from the Master Link File.

Behavioral healthcare provider data. Data requests to behavioral healthcare treatment providers will be conducted on a monthly basis. To facilitate the requests and maintain confidentiality, providers will be given a Treatment Code number (not the Research ID) at the start of the study for individuals receiving services at their agency. The Provider Data Request Form (included in the Appendix), will include only the Treatment Code; no participant name or Research ID will appear on the form or in the email requesting the data. Completed forms will be uploaded by the provider to TCU Box and available for download by authorized project staff. Data from the forms will be entered into a provider data tracking Microsoft Excel file at the IBR. The Treatment Code will be maintained in the Master Linking File that will be encrypted and stored at the IBR on a secure computer separate from any other participant data.

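### Opioid self-report over the last few days is compared with agency drug tests listed by month; no pairing rule is stated and no specimen date is among the listed form items

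*Combined protocol and SAP*

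**What the plan says.** In the combined protocol and SAP, section 14 (Data Analyses, Analyses of Secondary outcomes) states that "Validation of recent (last few days) self-reported opioid use will be compared with drug testing outcomes at each assessment time point". The statistics named are McNemar's test, sensitivity, specificity and kappa. Surveys fall at baseline, week 6 and week 12.

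No specimen collected by the study is described, and the study has no in-person contact. The tests are those in "agency records from police and BH providers (including intake and during-program UA test results" (section 14, Aim 2), and the secondary analyses also compare "urinalysis (UA) results from agency drug screens between the two groups".

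The Agency Records part of the study procedures lists what providers report. The drug test item is "Drug test results for this month". The same list asks for treatment initiation and discharge dates. Section 16 adds: "Data requests to behavioral healthcare treatment providers will be conducted on a monthly basis".

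For the week 6 survey, "Participants will be contacted in week 5 by the RA to schedule a date and time"; week 12 follows the same procedure. Neither is tied to a test date. At baseline, the research assistant's phone meeting is to take place "within 4 days of the ODP intake for clients in OP treatment and within 4 days of discharge for clients in residential care" (section 13).

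**The concern.** A recall of a few days can be checked against a urine test only if the specimen was taken close to the survey. The wording of section 14 shows that this is intended, but the listed data items neither secure it nor allow it to be checked. No rule is given for choosing among several tests in a month, or for a survey with no test.

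An honest report of no recent use may then be paired with an accurate positive from weeks before. The pair counts as disagreement although nobody misreported. Without the survey-to-test gap, low agreement cannot be interpreted.

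Self-reported drug use is one of the Aim 2 data sources, and Aim 2 asks how well the measures perform. This is the only analysis described that checks self-report against drug tests.

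**Working it through.** The plan gives no target or expected value for sensitivity, specificity or kappa, so there is no figure to reproduce. The calculation below is an illustration that isolates the effect of timing.

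**Inputs from the documents:** N = 40; recall of a few days; test results listed by month; monthly requests to providers.

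**Assumptions not in the documents:**
- reports are honest and the assay is perfect;
- recall and detection both cover 3 days (the survey or test day and the 2 days before);
- a share s = 0.3 or 0.5 of participants use opioids;
- users use on a fraction u of days (0.1 to 0.9), with day-to-day correlation r = 0, 0.5 or 0.8;
- the survey and one test fall on random days of the same 30-day month.

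**Step 1, the gap.** With both days uniform on 30 days, the mean gap is 10 days. A pair falls within 3 days with probability (30 + 2×29 + 2×28 + 2×27)/900 = 198/900 = 22%.

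**Step 2, agreement at gap g.** Let q = 1 − u(1 − r). For a user:
- P(one window negative) = (1 − u)q²
- P(both negative) = (1 − u)q^(2+g) for g ≤ 2
- P(both negative) = (1 − u)q⁴[(1 − u) + u·r^(g−2)] for g ≥ 3

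Example: u = 0.1, r = 0.5, s = 0.5, g = 10.
- q = 0.95, and P(one window negative) = 0.9 × 0.95² = 0.81225.
- P(positive), all participants = 0.5 × 0.18775 = 0.0939.
- P(both negative), users = 0.9 × 0.95⁴ × (0.9 + 0.1 × 0.5⁸) = 0.6600; all participants = 0.5 + 0.5 × 0.6600 = 0.8300.
- P(both positive) = 1 − 2 × 0.9061 + 0.8300 = 0.0178.
- Sensitivity = 0.0178/0.0939 = 0.19.
- Observed agreement = 0.8478; chance agreement = 0.0939² + 0.9061² = 0.8299.
- Kappa = (0.8478 − 0.8299)/(1 − 0.8299) = 0.105. At g = 0 it is 1.00.

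**Step 3, averaged over the gap, range over s and r:**

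| Use days among users | Kappa | Sensitivity | Specificity |
|---|---|---|---|
| 10-30% | 0.23-0.61 | 0.30-0.69 | 0.85-0.97 |
| 50% | 0.58-0.84 | 0.70-0.88 | 0.86-0.96 |
| 70% | 0.73-0.96 | 0.84-0.97 | 0.90-0.99 |
| 90% | 0.91-1.00 | 0.95-1.00 | 0.96-1.00 |

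Same-day pairs give 1.00 throughout.

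**Step 4, by gap, at 10-30% of days.** Kappa is 0.10-0.57 for gaps over 7 days, 0.51-0.82 within 3 days and 0.80-0.93 within 1 day. Closer pairs reduce the timing error but do not remove it.

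**Step 5, how many close pairs.** With 1, 2 or 4 randomly timed tests in the month, the nearest lies within 3 days for 22%, 39% or 63% of surveys, or about 9, 16 or 25 of 40. The share positive runs from 4% to 50% over all scenarios, so these pairs hold about 0.4-4.4, 0.6-7.8 or 1.0-12.5 positives. With 2 positives, both self-reported, the exact 95% interval for sensitivity is 16-100% (lower limit √0.025 = 0.158).

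**McNemar's test** compares the two marginal proportions, so gaps with no trend in use do not bias it. It is affected if use shifts in one direction between specimen and survey. An example is an intake test paired with a residential client's baseline survey after discharge; a test near discharge would be closer.

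**The case against.** A reader might infer that the provider form records no specimen date. The documents do not support that. The form is in an appendix that was not available; the protocol lists the items it has space for, and a monthly reporting period does not mean that results arrive undated. Dates may also be obtainable later, because the consent is "to allow release of behavioral healthcare agency data from the substance use treatment provider". This stands. The missing pairing rule does not depend on it.

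A reader might also infer that no pair can be aligned. That goes too far. Outpatient clients are met by phone within days of program intake, intake test results are among the data sources, and the treatment initiation date could roughly date an intake test. Some outpatient baseline pairs may therefore be close. The plan does not state this as a matching method, and it does not help at weeks 6 and 12.

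The illustration rests on assumptions, with kappa from 0.23 to 1.00, so it shows what timing can do and not what to expect. The remedy also recovers only a limited number of close pairs. There may be fewer positives than shown, because the sample includes people whose problem is another substance. Both points are fair.

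Finally, this is a secondary analysis in 40 people, and no decision rule or listed effect size uses kappa. That limits the severity. The analysis will still produce figures that someone will read.

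**Conclusion.** The point holds as a minor one. The plan compares a recall of a few days with tests listed by month. It states no pairing rule, and the visible item list has no specimen date. Followed as listed, timing gaps lower mainly sensitivity and kappa, and specificity less, without any misreporting.

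The documents support the direction but not a size. Under the stated assumptions the loss is large for intermittent use and near zero for near-daily use.

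Two stronger conclusions are not supported. McNemar's test is not invalid in general; it is affected only by a one-directional shift in use. Disagreement in close pairs does not by itself show misreporting, since honest reports give kappa of only 0.51-0.82 within 3 days at 10-30% use days.

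**What to change.** (a) If the Provider Data Request Form lacks it, add the specimen collection date, and confirm that the opioid result is identified. Ask providers for the dates of results already received.

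(b) State in section 14:
- each survey is paired with the agency test nearest to it in date;
- surveys with no test are counted and reported;
- the distribution of gaps, the number of pairs and the number of positives are shown at each time point;
- agreement is shown for all pairs and for pairs within a window fixed before analysis, and neither result stands alone.

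(c) Add this sentence: *Disagreement in distant pairs will not be read as misreporting; disagreement in close pairs may still partly reflect timing and will be interpreted with that caution.*

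The cost is one extra form field, one request back to providers and a few sentences. The drawback is that close pairs and positives will be few, so close-pair sensitivity may not be estimable. Asking for the date on each monthly form is easier than recovering it afterwards.

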
Study Procedures: Provide a chronological description of the procedures, tests, and interventions that will be implemented during the course of the study. Indicate the number of visits, length of each visit, and the time it would take to undergo the

various tests, procedures, and interventions. If blood or tissue is to be collected, indicate exactly how much in simple terms. Flow diagrams may be used to clarify complex projects.

Research ID. After participants have electronically consented to participate on an Informed Consent document, they will receive the Qualtrics link to complete the Demographic Forms, and Contact Information Forms. Each participant, will then be assigned a Research ID that will be the only identification used on any project data. Because study participants are referred by the Diversion program to distinctly different forms of treatment (either outpatient or residential), the Research ID's will be based on two separate 3-digit series; 100 for participants in outpatient and 200 for participants released from residential. The Research ID will be written on the signed Informed Consent and entered into a Master Link File that will pair the participant name with the Research ID. This file will be kept on password protected laptops used by the RA and Coaches and password protected computers used by the PI and Project Coordinator at the IBR.

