Breach of confidentiality. This risk will be minimized with procedures to safeguard the confidentiality of participants include assigning Research ID's to subjects. This number will be used as an identifier for all study materials including the participant's responses to the surveys, data stored from existing records, qualitative data, and T-CAP telehealth session data. Data from the T-CAP telehealth app will be stripped of participant phone number by the Project Coordinator, and the Research ID will be entered into the dataset. Participants will only be identified using this number and data will be reported in aggregate only. Consent forms with participant study numbers will be kept in a locked filing cabinet in a locked room in the IBR offices, accessible by authorized researchers. Electronic research data will be encrypted and password protected. Participants will be made aware during the consent process and prior to every research session that all information provided is considered to be confidential. Further procedures to protect confidentiality are described below. Only authorized research staff will have access to the de-identified data. Only the PI and Project Coordinator will have access to the T-CAP app data with the phone number when it is downloaded to the IBR secure server. These same authorized researchers will also have access to qualitative interview data, behavioral healthcare provider data, Qualtrics survey data with Research ID, and case notes from the Coaches. The RA will use the Research ID for reporting scheduling information (electronic files and demographic forms) to the IBR research team, and the Coach will use the Research ID when reporting case notes to the research team (electronic and paper files).

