The first step in maintaining confidentiality is to assign each participant an arbitrary Research ID that will be used on all data for that participant. A Master Link File will be maintained by the PI, Project Coordinator, Coaches and the field RA that will include the participant's name, Research ID, and study phone number. Treatment Code (described below) will only be included in the Master Link File maintained by the PI and Project Coordinator. This file will be encrypted and stored at the IBR on a secure computer separate from any other participant data. The Master Link File will be password protected, stored electronically, and kept separate from all other data files. It will be accessible only to authorized project staff.

Surveys. The RA will need to have the Master Link File on their TCU-owned secure laptop computer for tracking participants and obtaining Research IDs to enter on project materials. The laptop will be protected by a strong password and the link file, a Microsoft Excel database, will be encrypted and protected by a strong password. Every time a participant comes to complete a survey battery, the RA will use the participant name to look up the Research ID in the database. This will bring up the name and Research ID for that participant. The RA will enter the Research ID on the Qualtrics survey battery or on the paper version alternative. Updated Master Link Files will be uploaded by the RA via TCU Box for download by the IBR authorized researchers (PI or Project Coordinator). Master Link Files will not be stored in a TCU Box folder.

The RA will instruct the participant not to put their name or other identifying information on any paper forms. The Demographics Form—completed only at baseline—includes questions on demographics and background information, and does not have any questions of a sensitive nature. When the participant returns the Demographics Form, it will be mailed to the IBR in an envelope with the Contact Information Form. In the event that the Baseline battery of assessments is completed on paper (this is a back-up option in the event that internet access is not functioning), the survey will be mailed to the IBR in a FedEx envelope, separate from the Demographics Form and Contact Information Form. Data collection on Qualtrics will not have other data that could be used to identify the participant. When

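### As described, the Coach caseload file holds names and phone numbers alongside referrals and session notes, and goes to TCU Box weekly with no step that removes the names

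*Combined protocol and SAP*

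**What the plan says.** Item 16, Data from Coaches, says that each Coach needs a "caseload tracking file with participants' name, Research ID, and phone number", which is to be "accessible on their TCU-owned secure laptop computers in a Master Linking file". The next sentence says that this Excel file "will be encrypted and protected by a strong password and used for documenting assertive referrals and other support services", and adds the case notes on the MI telehealth sessions. Then: "The tracking files maintained by Coaches will be uploaded to TCU Box on a weekly basis for the duration of the study". Downloaded copies are kept on a secure computer at the research institute (IBR), and "tracking files will be separate from the Master Link File".

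Other sections set these rules:

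- Study Procedures, Research ID: each participant is given a "Research ID that will be the only identification used on any project data".
- Item 13, Consenting Procedure: participants are to be told that the information collected is identified only by a random Research ID.
- Item 15, Breach of confidentiality: "the Coach will use the Research ID when reporting case notes to the research team".
- Item 16, opening paragraph: the Master Link File contains name, Research ID and study phone number, and is held apart from every other data file.
- Item 16, Surveys: the research assistant sends updated link files through TCU Box, but "Master Link Files will not be stored in a TCU Box folder".

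**The concern.** Keeping names apart from data works only if no data file carries the names. Read literally, the Coach paragraph describes a working file that is both the key and the data, and it travels off the laptop every week. Staff who follow that paragraph would upload named notes, and the assurance given at consent would then not be true of the Coach data.

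Breach of confidentiality is the first risk listed in item 15. Participants are clients of a police diversion program, and their sessions cover relapse concerns and treatment needs. A file that pairs their names with such notes is among the more sensitive records the study will create.

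**Working it through.** The plan gives no figure to reproduce, so the check sets the provisions side by side.

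1. **Identifiers.** The Coach tracking file has name, Research ID and phone number. The Master Link File held by Coaches has name, Research ID and study phone number. They are the same three items; only the PI and Project Coordinator hold a version that adds the Treatment Code.
2. **Study data.** The Master Link File is to hold none. The Coach tracking file holds referrals, support services and MI case notes.
3. **Consequence of 1 and 2.** As described, the tracking file is a link file with study data attached. Storing it apart from the Master Link File does not separate names from notes, because the names are already in it.
4. **Removal of identifiers.** App data have the phone number replaced by the Research ID. Provider forms carry a Treatment Code only. Interview transcripts are redacted. Surveys carry the Research ID. No comparable step is described for the Coach file before or after upload.
5. **Storage in TCU Box.** Storage there is ruled out for Master Link Files (item 16, Surveys) and for MI fidelity recordings (Study Procedures, T-CAP Intervention). For Coach tracking files the plan gives the weekly upload and the place where downloads are kept. It does not say whether the uploaded copy is deleted or whether it remains encrypted.
6. **Exposure.** From Study Procedures, T-CAP Intervention: 40 participants / 2 Coaches = 20 per caseload, which agrees with the stated 20. One readable file would therefore identify up to 20 / 40 = 50% of the sample, and both files up to all 40. With 7 planned sessions each, the ceiling on noted sessions is 20 × 7 = 140 per file. This is an upper bound: it assumes that every session takes place and is noted in this file, whereas the same section also has case notes written on paper scripts and entered in a Qualtrics checklist.

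**The case against.** The best counter-argument is that the plan intends two files and words this badly. Coaches are said to maintain a Master Link File, the identifiers are placed in a Master Linking file, the tracking files are called separate from it, and item 15 has Coaches report notes by Research ID. Together these could describe names in one file and notes in another. That reading is possible, and the documents do not settle it. But the Coach paragraph lists the identifiers as contents of the tracking file and then assigns the notes to that file. A Coach who followed it to the letter would upload names with notes, so the wording needs repair under either reading.

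Four stronger inferences are tempting and are not supported:

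- *That names and data are not separated anywhere in the study.* The survey, app, provider and interview streams each have their own coding or redaction step. The conflict is confined to the Coach stream.
- *That one leaked file identifies a whole caseload.* The file is stated to be encrypted and protected by a strong password, so it must also be opened. Using the Research ID to identify people in other datasets would need access to those protected files as well.
- *That the weekly upload breaks the TCU Box rule.* Even link files may pass through TCU Box; only storing them there is barred. On whether Coach copies remain there, the plan is silent, which is not a contradiction.
- *That the Aim 2 referral results are affected.* Coach records do feed that outcome (item 14), but counting referrals from a named file does not change the count.

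**Conclusion.** The point holds for the Coach data stream. On its plain wording, the Data from Coaches paragraph puts names and phone numbers in the file that holds referrals and MI notes and is uploaded weekly. That is inconsistent with the Research-ID-only rule in Study Procedures and item 13, with the case-note rule in item 15, and with the separation rule at the start of item 16.

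The exposure is up to 20 named participants per file, and up to 40 across both, conditional on a file being both leaked and readable. This rests on the literal reading and on the stated caseload of 20. The likelihood of a breach cannot be estimated from the documents. The case for change is participant protection at low cost. No estimate, test or effect size is affected.

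**What to change.** Rewrite the Data from Coaches paragraph around two separate files; two sheets in one workbook would still be one file.

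1. **Coach link file.** It holds name, phone number and Research ID, with no referral or session data. It follows the existing link-file rule: it may be transferred via TCU Box but not stored there. The same rule should cover how Coaches receive contact details for new participants, which now reach them in a tracking spreadsheet passed through TCU Box (Study Procedures, Baseline procedures and the scheduling steps that follow).
2. **Caseload log.** It holds referrals, support services and MI case notes under the Research ID only. This is the file uploaded weekly.

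Remove the mention of a Master Linking file from the description of the caseload file, and state that uploaded copies are deleted from TCU Box once downloaded. It would also help to say whether the uploaded copy remains encrypted.

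The cost is small: a revised paragraph, a second file template, and aligned wording in the baseline and scheduling text. Coaches would look up names in a second local file. The document is itself a modified plan, so any combined files already in use would need to be split too. No new staff or data collection is needed.
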